## 6.1.5 Kaplan-Meier Analysis

For time to event endpoints analyzed with a Kaplan-Meier method, analysis time points will be presented at 30 and 180 days. Unless otherwise specified, if a subject is event-free, their date of censoring will be considered as the date of last contact in the study. For Kaplan-Meier estimates presented with the corresponding 95% log-log confidence interval  $(L_{\hat{s}}, U_{\hat{s}})$ , Greenwood's estimate of the standard error will be used. The Kaplan-Meier estimate of the event rate,  $\hat{F}$ , may be computed as  $1 - \hat{S}$  and the corresponding 95% log-log confidence interval is as follows:

$$L_{\hat{F}} = 1 - U_{\hat{S}} \\ U_{\hat{F}} = 1 - L_{\hat{S}}.$$

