## 6.1.6 Missing Data

Unless otherwise specified, techniques will not be used to impute missing data. If a subject (or lesion) is missing a data point for any reason, that subject (or lesion) will not be included in that portion of the analysis. The number of data values available for each analysis will be reported so that the reader can assess the potential impact of missing data.

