## 6.1.9 Duplex Ultrasound Assessments

In the case that multiple duplex assessments (e.g., a duplex ultrasound was non-diagnostic, requiring a repeat ultrasound) of the target lesion are performed within the visit window, the first diagnostic duplex assessment will be used as the basis for analysis. In the cases where angiography data are available within a protocol-defined window, and duplex ultrasound assessment is not available, angiographic data will be used to determine the patency.

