## 6.3.8 Primary Patency, Primary Assisted Patency and Secondary Patency

Primary patency, primary assisted patency and secondary patency will be derived on a *per-lesion* level.

Primary patency is defined as the absence of target lesion restenosis evaluated by duplex ultrasound (i.e., peak systolic velocity ratio  $[PSVR] \le 2.5$ ) and freedom from clinically-driven target lesion revascularization. The primary patency success must meet success criteria for the both components of patency. If the lesion fails either component of the patency endpoint, the lesion will be considered a failure for the efficacy endpoint.

Primary assisted patency is defined as patency of the target lesion following endovascular reintervention at the target vessel site in case of symptomatic restenosis. This is a cumulative

patency rate including patent target lesion post re-intervention for restenosis at the given followup timepoint.

Secondary patency reports patency of the target lesion after treatment of a (re)occlusion of the index lesion. This is a cumulative patency rate, including re-intervention (restenosis or re-occlusion) at the given follow-up timepoint.

A Kaplan-Meier (KM) survival analysis as described in Section 6.1.5 will be used to estimate the patency rates including primary, primary asissted and secondary. The patency rates will be presented as the KM estimate of freedom from loss of patency at 30 days and 180 days post-procedure. The survival curves, the KM estimate, and the 95% confidence interval will be presented. Lesions will be censored at the day of last subject follow-up for the following senarios:

- Have 6 months follow-up but no analyzable duplex ultrasound data, and no clinicallydriven TLR
- Have no 6 months follow up but also have no event of interst.

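### SAP 6.3.8 gives no event date for a patency loss found on duplex, so the day-180 Kaplan-Meier figure can depend on when visits fall in the window; keeping lesions with unreadable scans at risk is a second, smaller effect

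*SAP*

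**What the plan says.** **Estimator.** SAP 6.3.8 defines primary patency per lesion as a PSVR of at most 2.5 on duplex together with freedom from clinically-driven TLR. A lesion that misses either part is a failure. For all three patency types, "The patency rates will be presented as the KM estimate of freedom from loss of patency at 30 days and 180 days post-procedure".

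**Censoring.** "Lesions will be censored at the day of last subject follow-up for the following senarios": the first scenario is "Have 6 months follow-up but no analyzable duplex ultrasound data" and no clinically-driven TLR; the second is no 6-month follow-up and no event. The general rule in SAP 6.1.5 is similar: for an event-free subject, "their date of censoring will be considered as the date of last contact in the study".

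**Event dates.** SAP 6.3.6 and 6.3.7 date TLR and TVR from the revascularization date. No section dates a loss found on duplex.

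**Windows.** SAP 6.1.8 sets days 23-37 and 166-194, on both sides of the two read-outs.

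**Related rules.** Under SAP 6.1.6 a missing data point means "that subject (or lesion) will not be included in that portion of the analysis", unless otherwise specified. Under SAP 6.1.9, when duplex is repeated in the window, "the first diagnostic duplex assessment will be used as the basis for analysis". If duplex is not available but an in-window angiogram is, "angiographic data will be used to determine the patency". Follow-up angiography is done only for symptoms requiring intervention (Protocol 6.7, 6.8 and Table 6-1).

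**The concern.** Kaplan-Meier counts an event on the day it is recorded. A restenosis that may have developed at any time since day 30 becomes visible only at the 6-month scan. Scan date, midpoint between scans and nominal visit day are all open to the programmer. With the scan date, a loss found on day 181 or later is absent from the day-180 estimate. A patent lesion censored at an early visit leaves the risk set while later losses are still being counted. The first effect raises the estimate and the second lowers it.

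The censoring rule adds to this. A lesion without a readable 6-month scan has unknown duplex status, yet it stays in the denominator while other lesions' 6-month losses are counted.

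At stake is a named 6-month endpoint, presented with curves and a 95% interval that does not reflect either effect. Two analysts following the SAP could report figures more than ten points apart from the same data.

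**Working it through.** The plan states no patency rate, so there is no figure of its own to reproduce.

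**Inputs.** From SAP 6.1.8 and 6.3.8: windows of 15 days (23-37) and 29 days (166-194), read-outs at days 30 and 180. Assumed: true primary patency 95% at 30 days and 80% at 6 months; 140 lesions; no TLR; unreadability unrelated to loss. The share lost between the two scans is then q = 15/95 = 0.1579.

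**1. Event date, evenly spread visits, all scans readable, losses dated at the scan.**
- Patent lesions followed past day 180: only losses scanned on days 166-180 count, 15 of 29 days. 0.95 × (1 − 0.1579 × 15/29) = 87.2%.
- Patent lesions censored at their visit: on day t the lesions not yet scanned number (195 − t)/29 of those entering the window, so the daily factor is 1 − q/(195 − t). Over days 166-180 the divisor runs from 29 to 15 and the product is 0.8935. 0.95 × 0.8935 = 84.9%.
- Day 30: 1 − 0.05 × 8/15 = 97.3% against a true 95%.

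**2. Other visit patterns** (simulation of 140 lesions; early and late visits reproduced with a standard deviation of 5 days, cut to the window):

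| Visits | Patent censored at visit | Patent followed past day 180 |
|---|---|---|
| Even | 85% | 87% |
| Mean day 175 | 71% | 82% |
| Mean day 178 | 80% | 85% |
| Mean day 185 | 92% | 92% |

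The 6-month visit is the last one scheduled, so for early visits the left column is closer to the SAP's censoring wording.

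**3. Unreadable scans.** Let u be the unreadable share, with last follow-up at the 6-month visit. The daily factor becomes 1 − (1 − u)q/(195 − t).
- Even visits, u = 10%: 0.95 × 0.9037 = 85.9%. With u = 20%: 0.95 × 0.9140 = 86.8%. Against 84.9% this is about +1 and +2 points. Simulation gave +1.0 to +2.4 points with even visits and +0.5 to +1.1 with late visits. Both ranges are below one standard error (about 3.4 and 2.3 points).
- If every visit falls on day 180 and all loss appears at 6 months, the estimate is 1 − (1 − u) × 0.20, which is 82% and 84%. The size therefore depends on assumptions as well.

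**4. The two interact.** With early visits censored at the visit, u = 10% and 20% move the estimate from 71% to 73% and 76%, towards the truth. Removing the unreadable lesions at their last imaging, without changing the event date, takes it back to 71%.

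**5. Paired rule.** Put losses and patent results on nominal day 180 and let unreadable lesions leave just before. The day-180 risk set is then the readable lesions only: 0.95 × (1 − 0.1579) = 80.0%, for any in-window pattern and any u. Simulation gave 79.8-80.1% in every pattern with 0-20% unreadable.

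**The case against.** The strongest reply is that little here is an error. SAP 6.1.6 allows exceptions, and SAP 6.3.8 is one. A reader might infer that the two sections contradict each other; they do not. Censoring at last follow-up also agrees with SAP 6.1.5. That stands: the unreadable-scan rule is a questionable choice with a small effect.

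The SAP also does not say that losses are dated at the scan, and every figure above needs an assumed visit pattern. That stands too. A reader might infer that the plan always flatters the device. The documents do not support this, because early visits can lower the estimate and some patterns cancel. But leaving the date open does not protect the estimate: the scan date is one natural choice, and nothing rules it out.

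The safeguards help only in part. SAP 6.1.9 has the repeat-scan and angiogram rules, the core laboratory gives feedback on image quality (Protocol 12.1), and under SAP 6.1.6 "The number of data values available for each analysis will be reported". None sets an event date. A silent restenosis with an unreadable scan would not normally get an angiogram.

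Finally, a reader might infer that device clearance or trial success is affected. It is not. Secondary endpoints are descriptive (Protocol 8.3, SAP 6.3), success rests on the two primary endpoints (SAP 6.2), and the 30-day primary endpoint report supports the 510(k) submission (Protocol 9.6, SAP 3).

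**Conclusion.** The concern holds, with the missing event date as the main defect. If losses are dated at the scan, a true 80% reads about 85-87% with even visits, 92% with late visits and 71-82% with early visits, and there may be no net bias in between. The unreadable-scan rule adds about 1-2 points with 10-20% unreadable and even visits. The two should be corrected together.

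These sizes are illustrative. They rest on the assumed patency rates, 140 lesions, the visit patterns, and unreadability unrelated to loss. Assisted primary and secondary patency were not simulated. The point deserves a change before database lock because the endpoint is named and the remedy is cheap, but it does not threaten the trial's conclusions on its primary endpoints.

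**What to change.** Adopt these together in SAP 6.3.8.

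1. **Dates.** Assign nominal day 30 or 180 to losses and confirmed-patent results from in-window imaging, whether duplex or the angiogram allowed by SAP 6.1.9. Order losses before censorings. Keep actual dates for TLR and for losses found on unscheduled imaging.
2. **Censoring.** A lesion with no analyzable in-window 6-month imaging and no earlier event leaves the risk set at the earlier of last contact and day 179. If its 30-day scan was also unreadable, it leaves at its last analyzable imaging. In simulations with 3-5% TLR between visits, which set out-of-window scans aside, day 179 read 79.8-80.2% and censoring at last imaging read 78.4-79.1%.
3. **Out-of-window scheduled scans.** Keep losses seen on them as failures, as SAP 6.3.8 requires. Report an interval-censored sensitivity analysis on all actual scan dates, with the numbers of unreadable and out-of-window scans. A piecewise-constant hazard cut at day 30 read 79.7-80.6%, although the simulated truth had that form. The unrestricted nonparametric version read 77.1-82.6% and was unstable when scans cluster.
4. **Events.** Define the event separately for primary, assisted primary and secondary patency, because re-intervention is a failure only for primary patency.

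Item 3 leaves some bias in the main estimate. With actual dates and 5-20% of 6-month scans outside the window, late scans read 80.7-82.9% and early ones 79.4-77.2%, which is why the sensitivity analysis is needed. Dropping such losses is not safer. If a quarter of the later losses were scanned early and every patent lesion in window, dropping them would give 0.95 × (1 − 11.25/91.25) = 83.3%.

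The cost is SAP wording and a small programming change, with no new data. The figure may be less favourable and the interval slightly wider (simulated standard error 3.4 points with all scans readable, 3.9 with 20% unreadable).

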## 6.4 Analysis of Adverse Events (AE)

The AE analyses will be presented in the ITT set. All analyses will be descriptive with no inferential statistical test.

For AE reporting, the primary analysis will be based on subject counts. A subject with more than one event will be counted only once toward the event rate based on the total number of subjects with AEs. An event count will also be presented. For example, if a subject experiences one major unplanned amputation of the treated limb and two clinically-driven TLRs within 30 days, the subject will be counted once in the rate of total subjects with a 30-day MAE; the same subject will be counted once in the individual event category of "Major Unplanned Amputation of the Treated Limb" and twice in the "Clinically-Driven TLR" category.

A by-subject listing of all AEs will be provided.

## 6.5 Other Analyses

## 6.5.1 Screening Failures

Those patients who fail screening will be tabulated with their reason(s) for screening failure.

## 6.5.2 Subject Disposition

Subject accountability and study discontinuation will be summarized for the ITT set. Subject accountability at each protocol required visit will be summarized as the number of subjects with complete visits, missed visits, or study discontinuations prior to the visit.

All subjects who do not complete the study will be tabulated by reason for discontinuation. Additional variables summarized may include total study duration, study completion status, and the primary reason for study discontinuation.

## 6.5.3 Demographic and Baseline Characteristics

Demographic and baseline characteristics will be summarized for the ITT and mITT Sets. Demographic and baseline characteristics include but not limited to age, sex, race, and ethnicity, height, weight, blood pressure, ABI, and Rutherford stage.

## 6.5.4 Medical History

Medical history will be summarized for the ITT Set.

## 6.5.5 Poolability Across Investigational Sites

This study is designed and conducted as a multicenter clinical trial. Data from all the sites will be pooled. All subjects will be treated and evaluated following the same protocol to ensure generalizability of the study results.

A list of variables such as baseline demographics and lesion characteristics will be compared across sites to assess the appropriateness of pooling data from across all sites.

#### 6.6 Changes in Planned Analyses

Deviations or changes from this SAP deemed necessary due to violation of critical underlying statistical assumptions, data characteristics, or missing data will be clearly described with justification and rationale.

#### 7 **REVISION HISTORY**

Version	Date	Description
А	18June2018	Initial Release
В	14Sep2018	Revision after FDA questions
С	18Feb2020	Added statistical analysis by product power type (Pneumatic System and Electric System)
